6.7 Safety

6.7.1 Extent of Exposure

Duration of exposure will be defined in days as:

(date of last dose - date of first dose) + 1.

Duration of exposure will be summarized using descriptive statistics for each treatment group for the enrolled population.

6.7.2 Adverse Events

All AEs recorded on the eCRF will be coded using the MedDRA dictionary [Version 21.1 (or a later version if updated during the study)] and classified as treatment – emergent AEs (TEAEs) as follows:

• TEAEs are events with start date on or after the date of first dose of IMP and up to 14 days after the last dose of IMP or events with start date prior to the date of first dose of IMP whose severity worsens on or after the date of first dose of IMP on INSO11-17-115.

All AE data will be listed by treatment group. Treatment-emergence status will be flagged in the listing. In addition, corresponding listings of treatment-emergent serious AEs (TESAEs), AEs leading to permanent discontinuation of IMP and AEs resulting in death will be produced. AE ongoing or worsened from INS011-16-085 will be listed.

Summary tables of TEAEs by treatment group and overall will be produced for the enrolled population. No statistical comparisons of AEs between treatment groups will be performed.

The severity of all AEs is recorded as mild, moderate, or severe. If severity is missing for a TEAE, it will be considered severe.

The relationship between an AE and IMP treatment is assessed as definite, probable, possible, unlikely or not related. A treatment-related AE is an AE considered by the investigator as definitely, possibly, or probably related to IMP treatment or with unknown/missing relationship to IMP treatment.

An overview table will summarize the number and percentage of patients with at least one of the following TEAEs, where patients with more than one TEAE in a particular category are counted only once in that category:

Sponsor Name: Insys Development Company, Inc.

Sponsor Protocol ID: INS011-17-115 Covance Study ID: 000000163385

- any TEAE;
- TEAE by severity (mild, moderate, severe);
- treatment-related TEAE;
- severe treatment-related TEAE;
- TESAE;
- TESAE by severity;
- treatment-related TESAE;
- TEAE leading to study drug discontinuation.

The overview table will be repeated to summarize the number of TEAEs (displaying the number and percentage of observed events).

The number and percentage of patients reporting each AE will be summarized by System Organ Class (SOC) and Preferred Term (PT) for all enrolled patients. Tables will be sorted alphabetically by SOC. PTs will be sorted by descending overall total. The following summaries will be produced:

- TEAEs, by SOC and PT;
- TEAEs related to IMP treatment, by SOC and PT;
- TEAEs by relationship to IMP treatment, by SOC and PT;
- TEAEs by maximum severity, by SOC and PT;
- TEAEs related to IMP treatment by maximum severity, by SOC and PT;
- TEAEs causing discontinuation from IMP treatment, by SOC and PT;
- TEAEs related to IMP treatment causing discontinuation from IMP treatment, by SOC and PT;
- TESAEs, by SOC and PT;
- TESAEs related to IMP treatment, by SOC and PT;
- TEAEs leading to death, by SOC and PT.

In the above summaries, patients with more than one TEAE within a particular SOC are counted only once for that SOC. Similarly, patients with more than one TEAE within a particular PT are counted only once for that PT. For summaries by maximum severity, patients with multiple TEAEs within a particular SOC or PT will be counted under the category of their most severe TEAE within that SOC or PT. TEAEs with missing intensity/severity will be included (as severe) in the overall count of patients with TEAEs, but will not be included in the counts of patients with TEAEs within a SOC or PT.

Sponsor Name: Insys Development Company, Inc.

Sponsor Protocol ID: INS011-17-115 Covance Study ID: 000000163385

6.7.3 Laboratory Evaluations

6.7.3.1 Standard Safety Laboratory Panel

Data for the following hematology, blood chemistry, and urinalysis analytes received from central laboratory will be listed and summarized by treatment group and visit. If data for any additional analytes are also received or recorded, then these will be listed only.

Hematology	Serum Chemistry	Urinalysis
Hemoglobin	Albumin	pH
Hematocrit	Blood Urea Nitrogen	Specific Gravity
Total Leukocyte Count	Creatinine	Protein
Differential Leukocyte Count	Total Bilirubin	Glucose
Red Blood Cell Count	Alkaline Phosphatase (ALP)	Ketones
Platelets	Aspartate Transaminase (AST)	Bilirubin
Neutrophils (abs, %)	Alanine Transaminase (ALT)	Blood
Lymphocytes (abs, %)	Sodium	Nitrite
Monocytes (abs, %)	Potassium	Leukocyte Esterase
Eosinophils (abs, %)	Chloride	Urobilinogen
Basophils (abs, %)	Lactate Dehydrogenase (LDH)	Color and Clarity
White Blood Count	Uric Acid	Microscopic
	Glucose Calcium	Urine T. Protein, Random
	Çaldani	Urine Creatinine, Random

All laboratory data will be reported in conventional units. Out-of-reference-range values will be flagged as high (H) or low (L) in the listings.

For analysis purposes, values preceded by a "<" or a ">"sign (i.e. those below or above the limits of quantification) will be considered equal to the lower or upper limit of quantification, respectively.

Laboratory and urinalysis data will be summarized by visit using standard descriptive statistics for the enrolled population. Changes from baseline will also be summarized.

For hematology and serum chemistry, shift tables presenting movement in and out of reference ranges from baseline to each scheduled post-baseline visit will be

Sponsor Name: Insys Development Company, Inc.

Sponsor Protocol ID: INS011-17-115 Covance Study ID: 000000163385

provided for each treatment group. Corresponding shift tables will be produced for urinalysis.

6.7.3.2 **Urine Drug Screen**

A urine sample for the following assessments will be collected at study entry and end of study/early withdrawal: amphetamines, barbiturates, benzodiazepines, cocaine, opiates, phencyclidine and tetrahydrocannabinol.

Results from the urine drug screen will be listed for the enrolled population.

6.7.3.3 **Urine Pregnancy Test**

A urine dipstick pregnancy test will be performed on all female post-menarchal patients at Visit 1 and Visit 7 (End of Study) or early withdrawal.

Pregnancy screen results will be listed for the enrolled population.

6.7.4 Vital Signs

The following vital signs will be listed and summarized by treatment group and visit.

- systolic blood pressure (mmHg);
- diastolic blood pressure (mmHg);
- pulse rate (bpm);
- body temperature (°C);
- respiratory rate (breaths/min);
- weight (kg)
- height (m)
- BMI (kq/m^2).

Vital signs data and changes from baseline in vital signs will be summarized by visit using standard descriptive statistics for the enrolled population. Shift tables will also be presented from baseline to outside normal range criteria.

All vital sign data collected for the enrolled population will be listed.

6.7.5 Electrocardiograms

The following quantitative ECG measurements will be taken during the study:

- Heart rate (bpm);
- PR interval (msec);
- QRS interval (msec);
- QT interval (msec);

Sponsor Name: Insys Development Company, Inc.

Sponsor Protocol ID: INS011-17-115 Covance Study ID: 000000163385

- QTcF interval (msec)
- RR interval (msec).

An overall Investigator assessment of ECG will be provided (categories "normal", "abnormal, not clinically significant" and "abnormal, clinically significant").

The ECG measurements and changes from baseline in ECG will be listed and summarized by treatment group and visit using standard descriptive statistics for the enrolled population.

The Investigator assessment will be listed and the number and percentage of patients within each assessment category will be tabulated by treatment group and visit for the enrolled population. Shifts from baseline at each post-baseline visit will be presented.

A listing of ECG measurements and findings will be produced for all enrolled patients.

6.7.6 Physical Examination

Physical examination results (normal/abnormal) and details of abnormalities (Abnormal, Not Clinically Significant and Abnormal, Clinically Significant) will be listed for all enrolled patients.

For each physical examination body system, the number and percentage of patients with abnormalities at baseline and post-baseline will be summarized by treatment group for the All Enrolled Population. Shifts from baseline according to normal and abnormal criteria will also be presented for all patients

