6.1.7. Adverse Events and Serious Adverse Events

6.1.7.1. Definition of Adverse Events

An AE is defined as any untoward medical occurrence in a patient administered a pharmaceutical product during the course of a clinical investigation. An AE can therefore be any unfavorable and unintended sign, symptom, or disease temporally associated with the use of an investigational product, whether or not thought to be related to the investigational product.

Patients will be monitored throughout the study for AEs. Monitoring for treatment-emergent AEs will begin as soon as the patient is dosed. All AEs must be followed until they are resolved or stabilized, or until all attempts to determine resolution of the event are exhausted. The investigator should use their discretion in ordering additional tests as necessary to monitor the progress of such events.

An AE may be:

- A new illness, not documented in the patient's s medical history;
- Worsening of a concomitant illness;
- An effect of the study medication; it could be an abnormal laboratory value, as well as a significant shift from baseline within normal range which the qualified investigator or medical qualified designate considers to be clinically important;
- A combination of two or more of these factors.

Surgical procedures themselves are not AEs. They are therapeutic measures for conditions that required surgery. The condition for which the surgery is required is an AE, if it occurs or is detected during the study period. Planned surgical measures permitted by the clinical study protocol and the conditions(s) leading to these measures are not AEs, if the condition(s) was (were) known before the start of study treatment. In the latter case, the condition should be reported as medical history.

Absence seizures will not be considered AEs. However, new seizure types and injury resulting from a seizure will be captured as AEs.

Patients will be monitored throughout the study for AEs. All AEs must be followed until they are resolved or stabilized, or until all attempts to determine resolution of the event are exhausted.

The investigator should use his/her discretion in ordering additional tests as necessary to monitor the progress of such events.

Adverse events reported prior to dose administration will be recorded as part of the patient's medical history.

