8.5.3.5. Physical Examination Findings

Physical examination body systems will be presented as the number and percentage of patients that have normal or abnormal results at each visit. The examination will include evaluation of height, weight, general appearance, skin, eyes, ears, nose, throat, neck, lymph nodes, chest, heart, abdomen, and extremities.

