3.1 Safety Endpoints

The safety endpoints for this study are:

- Incidence, type and severity of adverse events (AEs) and serious adverse events (SAEs) associated with CBD, i.e. treatment emergent adverse events (TEAEs)
- Changes from baseline in vital signs, physical exam, ECG findings and laboratory values (hematology, chemistry and urinalysis)
- Change from baseline in weight

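### The physical-examination tables use only normal/abnormal, so worsening from not clinically significant to clinically significant is counted as no change

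*SAP*

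**What the plan says.** SAP 3.1 lists among the safety endpoints "Changes from baseline in vital signs, physical exam, ECG findings and laboratory values (hematology, chemistry and urinalysis"); Protocol 8.1 also includes the physical examination.

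SAP 6.7.6 plans three outputs:

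- A listing, in which "details of abnormalities (Abnormal, Not Clinically Significant and Abnormal, Clinically Significant) will be listed for all enrolled patients".
- A table by body system, in which "the number and percentage of patients with abnormalities at baseline and post-baseline will be summarized by treatment group".
- A shift table: "Shifts from baseline according to normal and abnormal criteria will also be presented for all patients".

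The binary scale is the protocol's own. The statistical methods in the protocol synopsis contain the same shift sentence, and Protocol 8.5.3.5 says: "Physical examination body systems will be presented as the number and percentage of patients that have normal or abnormal results at each visit".

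The ECG is handled differently. SAP 6.7.5 has the investigator rate it as normal, abnormal NCS or abnormal CS. It then says that "the number and percentage of patients within each assessment category will be tabulated by treatment group and visit for the enrolled population", with shifts from baseline at each later visit. Protocol 8.5.3.4 likewise keeps NCS and CS apart in the ECG shift.

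Baseline is Visit 10 of INS011-16-085 (SAP 6.1).

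**The concern.** The grade that separates an incidental finding from one that matters clinically is recorded, but no table uses it. The shift table is the only planned summary of within-patient change for this endpoint. In it, a patient who starts abnormal can only improve to normal or stay abnormal. The table of counts does not move either, because the patient is abnormal at both times.

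Long-term safety and tolerability is the study's only objective, and NCS findings at entry are plausible. Protocol 1.4 describes skin picking as part of the syndrome, and skin is one of the examined systems. Exclusion criterion 5 removes, on the investigator's judgement, patients with clinically significant disease that would jeopardise safety or validity, which makes NCS a more likely starting grade than CS. A reader who sees few shifts to abnormal could take this as reassurance that the table cannot give for patients who began abnormal.

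**Working it through.** The plan states no figure for this analysis, so there is none to reproduce. The check has two parts.

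**1. Which changes the binary table loses.** Three grades give nine baseline-to-later pairs. Three are no change on either scale. The other six are:

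| Baseline → later visit | Three grades | Normal/abnormal |
|---|---|---|
| Normal → NCS | worse | worse |
| Normal → CS | worse | worse (same cell as above) |
| NCS → CS | worse | **unchanged** |
| NCS → normal | better | better |
| CS → normal | better | better |
| CS → NCS | better | **unchanged** |

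One of three worsening transitions and one of three improving transitions disappear. The two remaining worsening transitions cannot be told apart. This follows from the definitions alone and needs no assumption about rates.

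**2. How many patients it might concern.** N = 66 is the maximum in SAP 2.3. The documents give neither of the next two inputs, so both are assumed over a range: s, the share of patients who are abnormal NCS in a given body system at baseline, and w, the chance that such a patient becomes CS.

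- Patients who cannot show worsening in the table: 66 × s = 6.6, 19.8 and 33.0 for s = 10%, 30% and 50%.
- Expected NCS-to-CS changes counted as unchanged: 66 × s × w.
- Probability of at least one such change: 1 − (1 − w)^n, with n = 66 × s rounded to 7, 20 or 33.

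| s | w = 2% | w = 5% | w = 10% |
|---|---|---|---|
| 10% | 0.13 patients; 13% | 0.33; 30% | 0.66; 52% |
| 30% | 0.40; 33% | 0.99; 64% | 1.98; 88% |
| 50% | 0.66; 49% | 1.65; 82% | 3.30; 97% |

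For example, at s = 30% and w = 5%, 66 × 0.30 × 0.05 = 0.99 and 1 − 0.95^20 = 64%. These values are per body system, and would be smaller with fewer patients than 66.

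The relevant share is the NCS share, not all baseline abnormality, because a system already CS cannot become CS on any scale. Suppose 60% are abnormal at baseline, and every patient not already CS has a 3% chance of becoming CS. The binary table shows at least one case with probability 1 − (1 − 0.03 × 0.4)^66 = 55%. If all 60% are NCS, the three-grade table shows one with probability 1 − 0.97^66 = 87%, a loss of about 32 points. If half of the 60% are already CS, it shows one with probability 1 − (1 − 0.03 × 0.7)^66 = 75%, and the loss is about 20 points.

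**The case against.** The strongest reply is that the SAP does what the protocol prescribes, that the information is not lost, and that three grades are a matter of preference.

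**Protocol source.** This stands. The synopsis and Protocol 8.5.3.5 set the binary scale. A reader might infer that the SAP cut down a richer protocol analysis; the documents do not support that.

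**Other routes.** These stand in part. A reader might infer that such worsening can never be seen. In fact the listing holds the grade for every enrolled patient. Protocol 6.1.7.1 also allows "Worsening of a concomitant illness" as an adverse event, and SAP 6.7.2 counts earlier events that worsen as treatment-emergent. But a listing is not a summary, and no text requires a CS examination finding to be reported as an adverse event.

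**Plan norm.** Laboratory and vital-sign shifts are also in-or-out of range, so the ECG is the exception. That is fair. However, SAP 6.7.3.1 and 6.7.4 also summarise numerical change from baseline for those measures, while the physical examination has no such second summary.

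**Sparse tables.** Also fair. Protocol 6.1.1 names 12 areas, and a 3 × 3 table has nine cells against four, for each dose group and visit.

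**Population.** Obesity and short stature are followed through weight, height and BMI (SAP 6.7.4), and hypotonia has no body-system row of its own. Skin is the clear case.

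A reader might also infer that the baseline and post-baseline wording in SAP 6.7.6 pools all later visits and so inflates abnormality. SAP 6.1 presents tables by visit where applicable, SAP 5.1 uses nominal visits, and Protocol 8.5.3.5 says each visit. Together they point to a by-visit display.

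**Conclusion.** The point holds for the tables. In the only change-from-baseline summary of this endpoint, NCS-to-CS worsening is recorded as no change, although the grade is collected and the same SAP keeps it for the ECG. That conclusion needs no assumption.

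The number of patients affected does rest on assumptions. Over the ranges used, 0.13 to 3.3 patients per body system would be counted as unchanged. Any probability of a missed case should be built on the NCS share at baseline; using all baseline abnormality overstates the loss.

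Severity is modest. Protocol 8.5.3 plans no inferential safety analysis, no decision rule rests on this table, and the listing and adverse-event reports give partial cover. It is a weakness of presentation shared by protocol and SAP, not a departure of one from the other.

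**What to change.** In SAP 6.7.6, replace the normal/abnormal shift with a shift on three grades (normal; abnormal NCS; abnormal CS). Present it for each body system, from baseline (Visit 10 of INS011-16-085) to each scheduled post-baseline visit, following the ECG approach in SAP 6.7.5. The protocol's normal/abnormal display can still be read from this table by adding the two abnormal categories.

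The cost is SAP wording, programming and a larger, sparser table. No new assessment in this study is needed, because SAP 6.7.6 already lists the grades.

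One condition must be checked first: whether Visit 10 of the parent study recorded NCS and CS, which these documents do not show. If it did not, keep the binary shift and add a table of the number and percentage of patients in each of the three grades by body system and visit. That keeps the defined baseline and still lets a reader see CS findings accumulate.

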6.8 Interim Analysis

No interim analysis will be performed for this study.

7. Changes in Planned Analysis

Not applicable.

8. Data Issues

Not applicable.

9. References

Sponsor Name: Insys Development Company, Inc.

Sponsor Protocol ID: INS011-17-115 Covance Study ID: 000000163385

Sponsor Name: Insys Development Company, Inc. Sponsor Protocol ID: INS011-17-115

ponsor Protocol ID: INS011-17-115 Covance Study ID: 000000163385

Appendix A: Schedule of Events

ASSESSMENTS		SA	FETY PERIOD		TAPER PERIOD	FOLLOW-UP PERIOD ^g	
Visit Number	l ^a	2, 3, 4 (monthly)	5, 6 (quarterly)	7 (End of Study)	Early Withdrawal	8	9 (Phone Call)
Study Time Points	Day 1	Weeks 4, 8, 12	Weeks 24, 36	Week 48		0-6 Days	30 Days After EOS
Visit Window (Days)	± 5	± 5	± 5	±3		± 3	± 5
Informed consent **	X						
Review of inclusion/exclusion criteria **	х			10			
C-SSRS	X			X	X		
Review concomitant medications	х	х	X	х	х	X	х
Vital signs ^b	X	X	X	X	X		
Clinical labs ^c	X	X	х	X	X		
12-lead ECG	X	Х	X	X	X		
Urinalysis	X			X	X		
Urine pregnancy screen for post-menarchal females	х			Х	х		
Urine drug screen	X			X	X		
Physical examination ^d	X	X	X	X	X		
Hyperphagia Questionnaire for Clinical Trial (HQ-CT)				Х	х		
Dosing with Cannabidiol Oral Solution	х	Х	Х	х	Xe	Xe	
Drug accountability	X	Х	X	Х	X	X	
AEs	X	X	X	X	X	X	X

Document Date: 04 October 2018

Sponsor Name: Insys Development Company, Inc.

Sponsor Protocol ID: INS011-17-115 Covance Study ID: 000000163385

ASSESSMENTS		SA	FETY PERIOD		TAPER PERIOD	FOLLOW-UP PERIOD ^g	
Visit Number	1ª	2, 3, 4 (monthly)	5, 6 (quarterly)	7 (End of Study)	Early Withdrawal	8	9 (Phone Call)
Study Time Points	Day 1	Weeks 4, 8, 12	Weeks 24, 36	Week 48		0-6 Days	30 Days After EOS
Visit Window (Days)	± 5	± 5	± 5	± 3		± 3	± 5
End of Study				X	$\mathbf{X}^{\mathbf{f}}$		

^{**} To be completed prior to enrollment into LTS, specifically within the 2-week period that is allotted post completion of Visit 10 (Study Completion) of INS011-16-085.

AE = adverse event.

Document Date: 04 October 2018

on 10/12/2022

^a For patients who enroll within the first 2 weeks after completion of Visit 10 (Study Completion) of INS011-16-085 protocol.

b Vital signs will be taken after a 5-minute seated rest.

^c If the total bilirubin laboratory value is abnormal, direct bilirubin will be drawn.

d The physical examination will include weight, and evaluation of general appearance, skin, eyes, ears, nose, throat, neck, lymph nodes, chest, heart, abdomen, and extremities.

Following the Safety Period or if the patient withdraws early, the patient will enter a Taper Period. Patients will be tapered off of Cannabidiol Oral Solution as follows: 40 mg/kg/day will be reduced to 30 mg/kg/day for three days, then 30 mg/kg/day will be reduced to 20 mg/kg/day for three days, then discontinued; 30 mg/kg/day will be reduced to 20 mg/kg/day for three days, then discontinued. This can be modified by the investigator based upon the patient's response.

fIf the patient withdraws prematurely from the Safety Period, all Visit 7 (End of Study) procedures should be conducted. Site staff will follow up with the patient 4 weeks after completion of treatment via the telephone to collect information regarding AEs and concomitant medications.

Follow-up Period Visit 9 will be a phone call.
